Dose Escalation Safety Lead-In and Mid-Study Interim Safety Analysis	
Dose Escalation Safety Lead-In
 
1. If, at any time, 1 or more of the first 3 safety-evaluable patients experience grade 3 or higher treatment-associated adverse events within the first 30 days of initiation of treatment, then no further patients will be enrolled at the current dose level.2. After 6 patients have been enrolled on study, enrollment will be halted for 30 days for completion of the dose escalation lead-in safety analysis. If 0-1 patients experience grade 3 or higher treatment-associated adverse events within the first 30 days of initiation of treatment, then additional patients may be enrolled at the next dose level.3. If enrollment is halted at any time during the lead-in period due to treatment-associated adverse events, the UCSF DSMB will review all available safety data with the Principal Investigator. Based on this review, study discontinuation or reduction of the epacadostat dose may be recommended. No further patients will be enrolled on study without the approval of the DSMB. If the DSMB allows additional patients to enroll, the lead-in period will be repeated at the new dose level with a maximum of 6 additional patients enrolled prior to follow-up safety analysis. At the discretion of the DSMB, patients who are currently on study may continue treatment at the reduced dose level.4. Patients who discontinue treatment on study within 30 days of initiation of therapy for reasons other than treatment-associated toxicity will be deemed inevaluable for safety and replaced for safety analysis. 
Mid-Study Interim Safety Analysis (Stage 1)
 
Enrollment will also be halted for 30 days for interim safety analyses after a total of 30 safety-evaluable patients have initiated treatment on study in both Arms A and B. Patients who discontinue treatment on study within 30 days of initiation of therapy for reasons other than treatment-associated toxicity will be deemed inevaluable for safety and replaced for safety analysis. The study will be discontinued under the following circumstance:
 
1. On-study occurrence of 3 or more Grade 4 (life threatening) serious adverse events (SAEs) or deaths, which are deemed at least possibly related to the study agent.2. Based on the review of data the DSMB has serious concerns about the safety of patients on the study. In addition to stopping the study, the DSMB may recommend that the epacadostat dose for all patients be de-escalated for all current and future patients or cessation of further patient accrual.

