4.2 Dose Expansion Schedule

Table 4-2: Dose Expansion Arms in both Stage 1 and 2

	Treatment Arms	N	Epacadostat	pembrolizumab	tavo-EP
Arm A	tavo-EP, pembrolizumab ad epacadostat	28*	MTD - as determine by dose escalation	200 mg via IV. Days 1 and 22 of each cycle for 6 weeks (42 days)	1/4 tumor volume at concentration of 0.5 mg/mL ¹ given intratumoral on Days 1, 5, 8 of each cycle for 6 weeks (42 days)
Arm B	tavo-EP and pembrolizumab	28			

*Patients in the dose escalation safety lead-in will have an opportunity to participate in Stage 1, Arm A per Investigator's discretion.

Rationale for cohort expansion: In the dose expansion cohorts, we will determine the tolerability of this combination, the recommended phase II dose (RP2D) and preliminary efficacy in 56 evaluable patients with recurrent or metastatic squamous cell carcinoma of the head and neck with tumors. Hence the cohort expansion warrants the confirmation of tolerability of this combination, was deemed safe will be pursued for further patients.

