4.3 Dose Limiting Toxicity (DLT) and Maximum Tolerated Dose (MTD)

If DLT is encountered during the first cycle, the following rules (see table below) will be applied. If no DLT is encountered at a given dose level, escalation will be continued to the next higher dose level. If no DLT is found at the highest cohort, this cohort will be considered the recommended Stage 1 dose for epacadostat.

Table 4-3: Dose Escalation Decision Rules - DLT and MTD

Number of Patients with DLT at a Given Dose Level	Escalation Decision Rule
0 out of 3	Escalate dose to next higher dose level
1 out of 3	Enter at least 3 more patients at this dose level If 0 of these 3 additional patients experience DLT (1 of 6), proceed to the next dose level If 1 or more of the 3 additional patients suffer DLT (2 of 6), then dose escalation is stopped and this dose is declared the maximal administered dose (highest dose administered) Determination of the MTD will continue at the next lowest dose cohort, at which an additional 3 patients will be added, for a total of 6 (unless that cohort already has 6 patients)

≥ 2 out of 3	Dose escalation will be stopped This dose level is declared the maximum administered dose The next lower cohort will be expanded to 6 patients If < 1 experience DLT, this dose is the maximal tolerated dose (MTD)
≤ 1 out of 6 at highest dose level below the maximum administered dose	This is generally the recommended Phase 2 dose At least 6 patients must be entered at the recommended Phase 2 dose

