5.2 Safety Stopping Rules

Clinical evaluations including laboratory and clinical safety assessments will be performed at 3-week intervals for patients who are actively receiving treatment on study. For patients in the follow-up portions of the study who are not actively receiving therapy, evaluations will be performed at 12-week intervals. Safety will be assessed during the study by documentation of adverse events (AEs), clinical laboratory tests, physical examination, vital sign measurements, and Eastern Cooperative Oncology Group (ECOG) performance status.

Lead-In Period and De-Escalation

1. If, at any time, 2 or more of the first 6 safety-evaluable patients experience grade 3 or higher treatment-associated adverse events within the first 30 days of initiation of treatment, then no further patients will be enrolled at the current dose level.
2. After 6 patients have been enrolled on study, enrollment will be halted for 30 days for completion of lead-in safety analysis. If 0-1 patients experience grade 3 or higher treatment-associated adverse events within the first 30 days of initiation of treatment, then additional patients may be enrolled at the current dose level.
3. If enrollment is halted at any time during the lead-in period due to treatment-associated adverse events, the UCSF DSMB will review all available safety data with the Principal Investigator. Based on this review, study discontinuation or reduction of the epacadostat dose may be recommended. No further patients will be enrolled on study without the approval of the DSMB. If the DSMB allows additional patients to enroll, the lead-in period will be repeated at the new dose level with a maximum of 6 additional patients enrolled prior to follow-up safety analysis. At the discretion of the DSMB, patients who are currently on study may continue treatment at the reduced dose level.
4. Patients who discontinue treatment on study within 30 days of initiation of therapy for reasons other than treatment-associated toxicity will be deemed inevaluable for safety and replaced for safety analysis.

Mid-Study Interim Safety Analysis

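### The synopsis closes a lead-in dose level at 1 event in the first 3 patients, section 5.2 only at 2 in the first 6, and no text says which rule governs

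*Combined protocol and SAP*

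**What the plan says.** The synopsis, in the row on the dose-escalation safety lead-in, closes the current dose level under item 1: "If, at any time, 1 or more of the first 3 safety-evaluable patients experience grade 3 or higher treatment-associated adverse events" within 30 days of starting treatment. After 0 or 1 such event in 6 patients, item 2 says "then additional patients may be enrolled at the next dose level".

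Section 5.2 has the same numbered list. Item 1 keeps the event, the 30 days and the consequence but reads "If, at any time, 2 or more of the first 6 safety-evaluable patients experience grade 3 or higher treatment-associated adverse events". After 0 or 1 event in 6, item 2 says "then additional patients may be enrolled at the current dose level". Item 3 is common to both lists: "If enrollment is halted at any time during the lead-in period due to treatment-associated adverse events, the UCSF DSMB will review all available safety data".

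Section 4.3 has a separate 3+3 scheme in Table 4-3. It counts DLTs, which section 4.3.1 defines over Cycle 1 and with listed exceptions. It escalates after 0 of 3. After 1 of 3 the instruction is "Enter at least 3 more patients at this dose level", with escalation if the total stays at 1 of 6. Table 4-3 is the only text that defines a maximum tolerated dose, and Table 4-2 gives Arm A's epacadostat dose as "MTD - as determine by dose escalation".

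The synopsis row on duration of therapy describes 6 patients at 300 mg, then 6 more at 600 mg if none of the first 6 has a DLT after 30 days.

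**The concern.** The lead-in's primary objective is safety, and it sets the epacadostat dose for Arm A. Two current texts give different closing thresholds for the same observation, and neither refers to the other. After one qualifying event in the first 3 patients, a site following the synopsis stops enrolling at that level, while a site following section 5.2 goes on to 6.

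The review in item 3 starts only when enrolment is halted for toxicity. Which threshold is applied therefore also decides whether that review takes place.

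**Working it through.** **The texts side by side.** Suppose 1 of the first 3 patients at 300 mg has a DLT that is also a treatment-associated grade 3 event within 30 days.

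- Synopsis item 1: close the level.
- Section 5.2 item 1: continue, closing only on a second event among the first 6.
- Table 4-3: enrol at least 3 more at this level.
- Synopsis, duration of therapy: escalation is described only for 6 patients without a DLT; 1 DLT is not addressed.

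Section 5.2 and Table 4-3 can both be obeyed. Synopsis item 1 cannot be obeyed together with Table 4-3, so following the stricter text does not resolve the conflict. The event definitions differ too. Section 4.3.1 exempts some grade 3 events, such as transient ALT/AST elevation. One such event in the first 3 closes the level under the synopsis, yet Table 4-3 counts 0 of 3 and escalates.

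**Where the synopsis and section 5.2 part.** With 2 or more events in the first 3, both close. With 0 in the first 3 and at most 1 in the next 3, neither closes. With exactly 1 in the first 3, the synopsis closes at once and section 5.2 continues. If none of the next 3 would have an event, the final decisions are opposite.

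**Probabilities.** The plan states no operating characteristic for either rule, so there is no figure to reproduce. Let p be the chance that a patient has a qualifying event, q = 1 − p, with patients independent. The documents give no p for the triplet. The assumed values are 10%, 12.5%, 20% and 30%; the second is the 1 in 8 quoted for anti-PD-1 alone in section 1.1.2.

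| | 10% | 12.5% | 20% | 30% |
|---|---|---|---|---|
| Exactly 1 of first 3: 3pq² | 24.3% | 28.7% | 38.4% | 44.1% |
| 1 in first 3, 0 in next 3: 3pq⁵ | 17.7% | 19.2% | 19.7% | 15.1% |
| Closed, synopsis item 1: 1 − q³ | 27.1% | 33.0% | 48.8% | 65.7% |
| Closed, section 5.2: 1 − q⁶ − 6pq⁵ | 11.4% | 16.7% | 34.5% | 58.0% |

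At p = 0.10, for example: 3 × 0.10 × 0.9² = 0.243; 3 × 0.10 × 0.9⁵ = 0.177; 1 − 0.9³ = 0.271; 1 − 0.5314 − 0.3543 = 0.114. The second row peaks at p = 1/6, at 20.1%.

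**Anchors in the documents.**

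- Tavo-EP plus pembrolizumab (Table 1-3, 22 patients): grade 3-4 pain 9.1% (2), cellulitis 4.5% (1) and AST 4.5% (1). That is 2 to 4 patients, depending on overlap. 3pq⁵ is 16.9% at 2/22 and 20.0% at 4/22. The table covers all adverse events, without epacadostat.
- Epacadostat 100 mg twice daily plus pembrolizumab (section 1.2.2): 18 + 99 = 117 patients. Treatment-related events of grade 3 or above were rash in 5 and four other terms in 2 each. That is 5 to 13 patients (5 + 4 × 2), leaving out terms seen in one patient only. 3pq⁵ is 10.3% at 5/117 and 18.5% at 13/117. There was no tavo-EP, and the dose is below the 300 mg starting dose.

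Neither source is the triplet or limited to 30 days.

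**Window.** Table 3-1 gives Cycle 1 as 42 days, and section 4.3.1 counts DLTs over Cycle 1. The enrolment hold is 30 days. A DLT in the remaining 42 − 30 = 12 days can fall after the escalation decision.

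**The case against.** The strongest reply is that the harm is bounded. Appendix 2 requires a written report of adverse events and DLTs at escalation, with written authorisation from the safety committee chair. DLTs must be notified to all sites, and dose levels confirmed for each patient. Section 5.2 adds weekly safety calls. The direct exposure is at most 3 further patients at the same dose after one event, which Table 4-3 already permits. This stands and lowers the severity. A reader might infer that patients could be escalated without review; Appendix 2 does not support that. But none of these safeguards states a threshold.

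A second reply is that the synopsis may be the updated text. It speaks of dose escalation, the next dose level and Arms A and B, while section 5.2 still speaks of de-escalation and the current level. The stricter trigger could be deliberate. That is an inference: the documents show neither that it was intended nor that the more permissive one was.

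A reader might also infer more from three details than they carry:

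- Counting 0 in the first 3 and 2 or more in the next 3 as a synopsis closure would raise its closure rates. Item 1 does not say so, and item 2 only withholds permission to escalate.
- The contrast between next and current dose level is not a strict opposition, since both statements are permissive.
- The 28-day cycles in Table 4-1 are a dosing-column header and define no third DLT window. The criterion of fewer than 1 DLT in one row of Table 4-3, against at most 1 of 6 in the next, may be a text-extraction slip. Both are side corrections.

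**Conclusion.** The contradiction is established from the wording alone: same event, same 30 days, same consequence, two thresholds and no order of precedence. Synopsis item 1 is also incompatible with the 1-of-3 row of Table 4-3.

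At assumed rates of 10% to 30%, the point of conflict is reached with probability 24% to 44%, and final decisions are opposite in 15% to 20%. The two anchors give about 17% to 20% and 10% to 19% for the latter. Closure under the rules as stated is 27% to 66% for synopsis item 1 against 11% to 58% for section 5.2. These figures assume independent patients with a common rate and are illustrative for the triplet. The point should be corrected by amendment; existing oversight reduces the risk but does not remove it.

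**What to change.** State one lead-in rule, counted per dose level, in identical words in both synopsis rows and in section 5.2.

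The default that best fits N = 3 in Table 4-1, the Arm A dose in Table 4-2 and Table 4-3 itself has two parts:

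- Table 4-3 on DLTs as the dose-setting rule.
- A stop with item 3 review when 2 or more of up to 6 patients at that dose level have treatment-associated events of grade 3 or above.

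The per-level count matters. If Table 4-3 escalates after 0 of 3, the first 6 patients on study are 3 at 300 mg and 3 at 600 mg, and the present wording would pool them.

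If the sponsor intended closure at 1 of 3, it should instead change section 5.2 and the 1-of-3 row of Table 4-3 to match.

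In either case, set one DLT window and make the enrolment hold equal to it. Check the at-most-1-of-6 criterion in Table 4-3 and the cycle length in Table 4-1 at the same time.

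The cost is amendment wording. Under the default, up to 3 more patients may be treated at a level after one early event. The lead-in may enrol 9 patients (3 + 6) rather than the expected 12; the synopsis already allows a minimum of 9. Choosing 42 days lengthens the hold by about 12 days per level; choosing 30 leaves it unchanged.

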Enrollment will also be halted for 30 days for interim safety analyses after a total of 30 safety-evaluable patients have initiated treatment on study. Patients who discontinue treatment on study within 30 days of initiation of therapy for reasons other than treatment-associated toxicity will be deemed inevaluable for safety and replaced for safety analysis. The study will be discontinued under the following circumstance:

1. On-study occurrence of 3 or more Grade 4 (life threatening) serious adverse events (SAEs) or deaths, which are deemed at least possibly related to the study agent.
2. Based on the review of data the DSMB has serious concerns about the safety of patients on the study. In addition to stopping the study, the DSMB may recommend

that the epacadostat dose for all patients be de-escalated for all current and future patients, or cessation of further patient accrual.

Safety review at participating sites

During the dose escalation safety lead-in phase of the study, weekly calls will be scheduled to review the safety data at all sites. Once the lead-in phase is completed, calls will be scheduled monthly. All sites with any active patients on study will be expected to have at least one representative on these calls. One or more representatives of the UCSF DSMC will be invited to participate as well.

6 Efficacy Assessments

MRI, contrast-enhanced CT, or PET/CT imaging of the face, neck, chest, abdomen, and pelvis are required at screening and on day 1 of each odd-numbered cycle excluding cycle 1. Both clinical and radiographic measurements may be used. All superficial, clinically apparent lesions that cannot be adequately assessed radiographically (e. g. subcutaneous lesions) must be numbered and photographed with a metric ruler visible in each photograph. For photographed lesions with borders that are not clearly visible, investigators should trace the lesions' outline, making a solid line with a felt-tipped pen. Visible lesions should never be circled with a solid line but dashed or dotted lines may be used to distinguish these markings from the borders of otherwise invisible lesions. Tumor assessments will be made using RECIST version 1.1. IL-12 plasmid dosing may be based on the most recent tumor measurements and measurements need not be repeated immediately prior to each tavo-EP treatment.

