11.1.1.1 Definitions

Evaluable for toxicity

All patients will be evaluable for toxicity from the time of their first treatment with epacadostat, pembrolizumab, or tavo-EP.

Evaluable for objective response

Only those patients who have measurable disease present at baseline, have received at least one cycle of therapy, and have had their disease re-evaluated will be considered evaluable for response. These patients will have their response classified according to the definitions stated below. (Note: Patients who exhibit objective disease progression prior to the end of Cycle 1 will also be considered evaluable).

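### Lead-in safety rule: a patient who leaves within 30 days for a non-toxicity reason is replaced even after a grade 3 or higher treatment-associated event, so an observed event can leave the halt count

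*Combined protocol and SAP*

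**What the plan says.** The lead-in rules stand in the synopsis (Dose Escalation Safety Lead-In) and in section 5.2 (Lead-In Period and De-Escalation), each as four items.

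- **Item 4, both places.** Patients who discontinue within 30 days of starting "for reasons other than treatment-associated toxicity will be deemed inevaluable for safety and replaced for safety analysis". The only test is the reason for stopping.
- **Item 1, the halt rule.** Section 5.2 stops enrolment at the current dose level if "2 or more of the first 6 safety-evaluable patients experience grade 3 or higher treatment-associated adverse events within the first 30 days". The synopsis uses a different threshold: "1 or more of the first 3 safety-evaluable patients experience grade 3 or higher treatment-associated adverse events". Both are limited to safety-evaluable patients and both apply at any time.
- **Item 2, the continue rule.** "If 0-1 patients experience grade 3 or higher treatment-associated adverse events within the first 30 days of initiation of treatment", more patients may be enrolled (at the current dose level in section 5.2, at the next one in the synopsis). This item says patients, without the qualifier used in item 1.
- **Interim, synopsis and section 5.2.** Enrolment pauses "after a total of 30 safety-evaluable patients have initiated treatment on study", and the item 4 sentence is repeated. The stopping criterion that follows is three or more Grade 4 serious events or deaths on study that are at least possibly related. It is not limited to evaluable patients.
- **Section 11.1.1.1.** "All patients will be evaluable for toxicity from the time of their first treatment with epacadostat, pembrolizumab, or tavo-EP".
- **Sections 7.2 and 7.6.** Safety is analysed in all treated subjects.
- **Sections 4.3 and 4.3.1.** The DLT rules contain no exclusion based on the reason for stopping.

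**The concern.** Whether a patient counts for the halt rule should depend on whether that patient informs the toxicity question. A patient who has already had a qualifying event does so, whatever happens next. Item 4 looks only at the recorded reason for stopping.

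The protocol leaves room for the two to differ. A grade 3 event need not end treatment: Table 4-4 allows agents to be withheld with a return within 6 weeks, and the paragraph on dose interruption allows holds of up to 6 weeks. Both run past the 30-day window. A patient on hold can therefore leave before day 30 for one of the other reasons in section 9, such as concurrent illness, the patient's own request or non-compliance.

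Safety is the primary objective of the lead-in, and the decision rests on about six patients. One event removed from the count can turn a halt into permission to go on. The same patient could count as a DLT, appear in the safety tables and still be inevaluable under item 4.

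**Working it through.** **Plan's own figure.** The documents state no operating characteristics for any safety rule, so there is nothing to reproduce.

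**Step 1: counting example (section 5.2 threshold).** Six patients start. Patient A has a grade 3 related event on day 10 and leaves on day 20 after withdrawing consent. Patient B, another of the six, has a grade 3 related event after A has left. A seventh patient replaces A and has no event.
- Literal item 4: A is removed, so the count is 1 of 6 evaluable and the halt threshold is not met.
- With A counted: 2 of 6, and enrolment halts.

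The order matters. If B's event comes while A is still on treatment, item 1 is met at once, and nothing in the text reverses a halt when a patient later leaves.

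**Step 2: model.** Let p be the true 30-day rate of grade 3 or higher treatment-associated events. Let s1 and s0 be the chances of stopping within 30 days for a non-toxicity reason with and without an event. All three are assumptions; the documents give no values.
- Literal rule, rate among counted patients: p(1−s1) / [p(1−s1) + (1−p)(1−s0)].
- Amended rule (events always count, only event-free leavers replaced): p / [p + (1−p)(1−s0)].
- Chance of halting at counted rate r: 1 − (1−r)^6 − 6r(1−r)^5.

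**Step 3: p = 0.30, s0 = 0.10.**
- s1 = 0.10: 0.27 / (0.27 + 0.63) = 0.300. Halt = 1 − 0.118 − 0.303 = 0.580, the same as with nobody removed.
- s1 = 0.20: 0.24 / 0.87 = 0.276. Halt = 0.526.
- s1 = 0.30: 0.21 / 0.84 = 0.250. Halt = 1 − 0.178 − 0.356 = 0.466.
- s1 = 0.50: 0.15 / 0.78 = 0.192. Halt = 0.326.
- Amended rule: 0.30 / 0.93 = 0.323. Halt = 0.627.

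**Step 4: range over the true rate.** Chance of at least 2 of 6, with s0 = 0.10:

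| True rate | s1 = 0.10 | s1 = 0.20 | s1 = 0.30 | s1 = 0.50 | Amended rule |
|---|---|---|---|---|---|
| 20% | 0.345 | 0.300 | 0.254 | 0.160 | 0.387 |
| 30% | 0.580 | 0.526 | 0.466 | 0.326 | 0.627 |
| 40% | 0.767 | 0.721 | 0.665 | 0.513 | 0.804 |

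For the synopsis threshold (at least 1 of 3) at a 30% true rate, the literal rule gives 0.657, 0.620, 0.578 and 0.473 for the same four values of s1, and the amended rule gives 0.689.

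**Step 5: what the model leaves out.** It takes the count among the final evaluable patients. Because item 1 applies at any time, some halts would be triggered before the patient leaves, so the literal-rule figures are lower limits on the halt probability. This matters most for the synopsis threshold, where a single event in a patient still on treatment already meets the rule.

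**Step 6: interim.** No calculation is needed. Evaluability sets when the 30-patient analysis takes place; the criterion itself counts events on study.

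**The case against.** The best defence is that item 4 defines a decision cohort, while sections 7.2, 7.6 and 11.1.1.1 define who is reported, and a trial may use both. Replacing patients who leave early without toxicity is ordinary practice. That is fair for event-free leavers. It does not explain why a patient with an observed event should be replaced, and the conflicting definitions of who is evaluable for toxicity remain.

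There are also safeguards. Item 2 is worded for patients in general, so with two affected patients its plain wording is not met. The DLT rules have no such exclusion. Appendix 2 requires a written report to the DSMC Chair before escalation, covering all adverse events and DLTs. These make a wrong decision less likely, but they leave items 1 and 2 giving different answers for the same patients. The DSMB review of all available data in item 3 begins only after a halt, which is the trigger that item 4 can weaken.

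Progression is a weak example of an early stop reason. The first on-treatment imaging is at cycle 3 day 1, after two 42-day cycles (day 85), entry requires a life expectancy of at least 4 months, and section 4.4.1 allows treatment beyond progression. Clinical decline and withdrawn consent remain possible.

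A reader might infer that the interim stopping rule loses events in the same way. The documents do not support this: that criterion is neither limited to evaluable patients nor tied to the 30-day window. A reader might also infer that the rule always favours judging the triplet safe. It does so only if non-toxicity stopping is more likely after an event; with equal rates the modelled halt probability is unchanged.

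**Conclusion.** The point holds for the lead-in. Read literally, items 1 and 4 together allow an observed grade 3 or higher treatment-associated event to leave the halt count, in conflict with section 11.1.1.1 and out of step with item 2. With six patients, one such removal can change the decision, provided the patient leaves before the threshold is reached.

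The effect on the halt probability is conditional. At a 30% true rate it ranges from none (equal stopping rates) to a fall from 0.580 to 0.326 (50% against 10%), on stopping rates that are assumed. Even with equal rates, observed events are discarded.

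The events do not vanish from the trial record: safety tables, DLT assessment and the escalation report keep them. At the interim, the repeated replacement sentence creates ambiguity only.

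**What to change.** 1. In item 4 of the synopsis and of section 5.2, state that a patient with a qualifying event in the window is counted whatever the reason for stopping, and that only patients who leave early without such an event are replaced.
2. Use the same term for the counted patients in items 1 and 2, and align both with section 11.1.1.1.
3. In the interim paragraphs of the synopsis and section 5.2, state that the replacement sentence sets only the timing of the 30-patient analysis and removes no event from the stopping count.

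The synopsis and section 5.2 also disagree on the item 1 threshold and on the dose level that item 2 opens. The sponsor must reconcile these; the counting sentence works with either version.

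No dose or event threshold changes. The text cost is one or two sentences in each place. The operating cost is that the lead-in halts more often, and not trivially: at a 30% true rate and 10% event-free stopping, 0.627, against 0.580 with nobody removed and 0.466 under the literal rule with 30% stopping after an event. It exceeds 0.580 because only event-free patients are now replaced.
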